## Data Collection Instrument 3 - Patient past medical history

Past Medical history	Key Name	Data Type	Values
Morbid Obesity (BMI>35)	МО	Binary	Yes/No. MO if BMI > 35
Diabetes Mellitus	DM	Binary	Yes/No
Cerebro-Vascular Disease	CVD	Binary	Yes/No
Chronic Obstructive Pulmonary Disease	COPD	Binary	Yes/No
Anticogulant/aggregant Medications	ACAM	Binary	Yes/No
Ischemic Heart Disease	IHD	Binary	Yes/No
Hypertension	НВР	Binary	Yes/No. HBP if sBP>140 or dBP >90
Liver Disease	LD	Binary	Yes/No
Chronic Kidney Disease	CKD	Binary	Yes/No. eGFR ≤59
Inmunosupression/Oral Corticosteroids/ Chemotherapy	CIS	Binary	Yes/No (on admission)
Radiotherapy	RTP	Binary	Yes/No
Endometriosis	END	Binary	Yes/No
Crohn's disease	CHRD	Binary	Yes/No
Abdominal malignancy	AM	Binary	Yes/No. Including Gynecologic origin
Abdominal malignancy origin	AMO	List	Colorectal/Gynecologic/Gastroesophageal/Hepatobiliary/Splenic/ Pancreatic/Urologic/Haematologic

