#### Inclusion and Exclusion Criteria

#### **Inclusion Criteria:**

Adult patients (≥16 years of age) admitted for mechanical small bowel obstruction. Example etiologies which should be included:

Adhesions.

Hernias with bowel compromise (incisional/parastomal, ventral, inguinal, femoral, obturator, internal).

Malignancy (primary: lymphoma, carcinoid, GIST, adenocarcinoma/metastatic disease: colon, ovarian, gastric, pancreatic, melanoma and others).

Enteroliths/gallstones/bezoars/foreign bodies

Radiation.

Inflammation (Crohn's disease, mesenteric adenitis, appendicitis, diverticulitis, tuberculosis, actinomycosis, ascariasis).

Congenital (malrotation, duplication cysts).

Trauma (hematomas, ischemic strictures).

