#### Missing data and retrospective patient entry

The online database has been designed to allow sites to securely access an individual patient's data throughout the study period. This means that any missing or erroneous data can be altered by the local investigators whilst the data collection period is ongoing. In order to maximize data completion and emphasize its importance to collaborators, participating Centers with >5% missing data in mandatory fields (i.e. less than 95% data completeness) will be excluded from the study.

The study design means that sites may retrospectively identify eligible patients that were missed primarily and for whom contemporaneous patient and operation data was not entered.

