### Data Collection Instrument 2 - Patient demographics

Demographics	Key Name	Data Type	Values
Country Code	СС	List	List of included countries (chain, number)
Center ID	CID	List	List of study centers (chain, number)
Patient ID	PID	Chain	Country code-Centre ID-patient number (chain, number)
Age (years)	AGE	Integer	Number
Sex	SEX	List	Male, Female
Body Mass Index	ВМІ	Integer	Weight (Kg) Height (Cm) BMI (integer)
Date of Admission	DOA	Date; time	Date of index admission dd/mm/yy hh:mm
Date of Discharge	DOD	Date	Date of discharge from hospital
Length of Stay	LOS	Integer	Number of Days (Integer; calculated from the admission and discharge date)
Cathegory	CAT	List	Ethiology (Adhesions, Bezoar, Gallstone ileus, Hernia (primary/internal/incisional/parastomal), Stenosis (anastomotic, inflammatory/endometriosis), Tumor (primary/carcinomatosis/Radiotherapy), congenital (malrotation)

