## Data Collection Instrument 7 - Initial Complementary Exams

Current Episode Initial Complementary Exams	Key Name	Data Type	Values
White Blood Cell Count	WBC	Integer	Number x10³
Hemoglobin	НВ	Decimal	Number (g/dL)
Potassium	К	Decimal	Number (mEq/L)
Creatinine	CRE	Decimal	Number (mg/dL)
CRP	CRP	Decimal	Number (mg/L)
INR	INR	Decimal	Number (mg/L)
Lactate	LAC	Decimal	Number (mg/dL)
Date First Plain Abdominal X ray	DFXR	Date; time	dd/mm/yy hh:mm
First AXr Stand up	FXRS	Binary	Yes/No
First AXr Air-Fluid Levels	FXRAF	Binary	Yes/No
First AXr Gastric Distension	FXRGD	Binary	Yes/No
First AXr Colonic Gas	FXRCG	Binary	Yes/No
Date Computed Tomography	DCT	Date; time	dd/mm/yy hh:mm
Computed Tomography Type	CTT	List	None; Without Contrast; IV Contrast; Oral Contrast; Double Contrast
CT Report Free Fluid	CTFF	Binary	Yes/No
CT Report Disminished Bowel Enhancement	CTDBE	Binary	Yes/No
CT Report Pneumatosis	СТР	Binary	Yes/No
CT Report Portal Gas	CTPG	Binary	Yes/No
CT Report Pneumoperitoneum	CTN	Binary	Yes/No
CT Report Small Bowel Wall Thickness	CTBWT	Decimal	Number (milimeters)
CT Report Small Bowel Diameter	CTSBD	Decimal	Number (Centimeters)
CT Report Feces Sign	CTFS	Binary	Yes/No (breadcrumb sign)
CT Report Peak Sign	CTPS	Binary	Yes/No (visible caliber change)
CT Report Whirl Sign	CTWS	Binary	Yes/No
CT Report Etiological Diagnosis	CTED	Binary	Yes/No (reported)
CT Report Diagnosis	CTE	Chain	Diagnosis (ie: single adhesion, matted adhesions, Hernia, Tumor)
AAST SBO	AAST	List	I, II, III, IV, V

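### The list for abdominal malignancy origin has no small-bowel and no other/unknown value, so a known small-bowel primary can only be left blank or coded to the wrong organ

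*Protocol*

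**What the plan says.** Data Collection Instrument 3 (past medical history) holds two linked fields. AM, abdominal malignancy, is binary, and its whole definition is "Yes/No. Including Gynecologic origin". AMO, the origin of that malignancy, has data type List with the values "Colorectal/Gynecologic/Gastroesophageal/Hepatobiliary/Splenic/ Pancreatic/Urologic/Haematologic".

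The inclusion criteria give examples of causes of obstruction that should be included. The malignant ones are "Malignancy (primary: lymphoma, carcinoid, GIST, adenocarcinoma/metastatic disease: colon, ovarian, gastric, pancreatic, melanoma and others".

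The cause of the current episode is recorded separately, in the category field (CAT) of Data Collection Instrument 2. Its tumour option reads "Tumor (primary/carcinomatosis/Radiotherapy), congenital (malrotation". The CT diagnosis field (CTE) in Data Collection Instrument 7 is free text: "Diagnosis (ie: single adhesion, matted adhesions, Hernia, Tumor".

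**The concern.** A closed list should hold a value for every patient who can reach it, or end in a catch-all. AMO does neither. It has a value for splenic origin but none for the organ that the study is about. A site with a patient known to have a small-bowel tumour must either skip the field or pick a neighbouring organ.

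The second choice does more harm. A blank is visible at analysis. A small-bowel tumour entered as colorectal looks like any other colorectal entry and adds to that count.

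At stake is the accuracy of one baseline characteristic. The primary objective sets out to explore differences in patients across the cohort, and cancer history is part of that description.

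**Working it through.** There is no figure in the plan to reproduce. The check sets the AMO list against the tumours named in the inclusion criteria, then looks for another field that could supply the origin.

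**Step 1: the list.** AMO has 8 values. Values naming the small bowel: 0. Values meaning other or unknown: 0.

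**Step 2: the named tumours.** The inclusion criteria name nine: four primary and five metastatic.

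| Named in the inclusion criteria | AMO value |
|---|---|
| Lymphoma | Haematologic |
| Colon | Colorectal |
| Ovarian | Gynecologic |
| Gastric | Gastroesophageal |
| Pancreatic | Pancreatic |
| Carcinoid | Depends on organ; none if small bowel |
| GIST | Depends on organ; none if small bowel |
| Adenocarcinoma | Depends on organ; none if small bowel |
| Melanoma | No skin value; whether AMO applies is unclear (see objection) |

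Five of nine always have a value. Three of nine have one only when they arise outside the small bowel, in a listed organ. The open-ended remainder at the end of the criterion has no catch-all to match it.

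**Step 3: does AM = Yes apply?** A previously known tumour of the small bowel is an abdominal malignancy on any reading of AM. Such a patient therefore reaches AMO and finds no fitting value.

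**Step 4: other fields.**
- CAT separates primary tumour, carcinomatosis and radiotherapy, but gives no organ.
- The previous SBO etiology field (PSBOE, Instrument 5) mentions primary tumour, again without an organ.
- Previous small bowel resection (PSBR, Instrument 5) is yes/no and is not tied to a tumour.
- First surgery category (FSC, Instrument 4) describes the type of operation, not the tumour.
- CTE and the surgical technique fields (FST, LST) are free text.

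No other coded field records tumour origin.

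**Step 5: result.** With no small-bowel value available, the recorded small-bowel share is 0% for every possible true share.

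**The case against.** The strongest reply is that the two lists serve different purposes. The inclusion criteria list causes of the present obstruction, whereas AMO sits among comorbidities such as diabetes and COPD and need not mirror them. No research question asks for the organ of origin, and the current cause is captured by CAT. Some origins could also be recovered from free text. All of this stands, and it keeps the point small. It does not supply a code for the patient in step 3, and free text is not a substitute for a coded value.

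A reader might infer more than the protocol supports:

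- **That every carcinoid and GIST is uncodable.** AMO codes organ, not histology. A gastric GIST fits Gastroesophageal and a colorectal carcinoid fits Colorectal.
- **That melanoma patients are miscoded.** AM can be read as cancers that originate in abdominal or pelvic organs. On that reading a skin primary gives AM = No and AMO does not arise. The protocol does not settle this, nor whether AM covers a tumour first found in this episode.
- **That a breakdown of malignant obstruction by tumour source is spoiled.** The protocol plans no such table, and AMO does not record the cause of the episode. A patient with past colorectal cancer and an adhesive obstruction also has AM = Yes and AMO = Colorectal.
- **That blanks could cost a centre its place.** The rule is that "participating Centers with >5% missing data in mandatory fields (i.e. less than 95% data completeness) will be excluded from the study". The protocol does not say that AMO is mandatory, and blanks in one conditional field would add little to a total taken over all such fields.

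**Conclusion.** The point holds in a limited form. AMO cannot record a small-bowel primary, or any other unlisted or unknown origin. For a known small-bowel primary the field will be blank or wrong, and the recorded share is fixed at 0%.

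The effect is confined to the malignancy-origin history variable. Incidence by broad etiology, through CAT, is not affected. The number of patients cannot be derived, because the protocol gives neither the expected share with AM = Yes nor the distribution of origins among them.

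The conclusion assumes that AMO is implemented in REDCap with the values shown in the protocol. It is a minor point, worth making because the misclassification is certain for these patients and easy to prevent.

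**What to change.** Add two values to AMO: Small bowel, and Other/unknown (specify). Then query all records already entered with AM = Yes, including those where AMO is filled, since a wrong organ cannot be told from a right one. The protocol already lets sites correct entries while data collection is open.

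The cost is two list values in REDCap and a short site query limited to patients with AM = Yes. Eligibility, patient management and the other instruments do not change.

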## Data Collection Instrument 4 - Patient past surgical history

Past Surgical history	Key Name	Data Type	Values
Previous abdominal surgery	PAS	Binary	Yes/No (excludes abdominoplasty and cesarean section)
Number of previous abdominal surgeries	NPS	Integer	Number (includes gyne and hernia surgeries)
Appendectomy	APP	Binary	Yes/No
Hernia surgery	HES	Binary	Yes/No
SBO surgery	SBOS	Binary	Yes/No
Previous peritonitis	PP	Binary	Yes/No
Date First Surgery (if one also the last)	DFS	Date	dd/mm/yy
First Surgery Technique	FST	Chain	Surgical technique
First Surgery Category	FSC	List	Predefined: CRS, GIS, HBPS, AWS, GIN, URO, VAS, AA (appendectomy)
First Surgery Laparoscopy	FSL	Binary	Yes/No (including conversion)
First Surgery Emergency	FSE	Binary	Yes/No
Date Last Surgery	DLS	Date	dd/mm/yy, Only in case >1 abdominal surgery
Last Surgery Technique	LST	Chain	Surgical Technique
Last Surgery Emergency	LSE	Binary	Yes/No
Last Surgery Laparoscopy	LSL	Binary	Yes/No (including conversion)
Time Last Surgery to Episode	TLSE	Calc	DOA (dd/mm/aa) - DLS (dd/mm/aa) = in Years

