### **Definitions**

**Mechanical small bowel obstruction (SBO):** An intrinsic, extrinsic or endoluminal process which narrows or occludes the bowel lumen and delays the passage of luminal contents.

**Ileus:** Functional motility disorder characterized by adynamic paralytic bowel, leading to many of the same symptoms of mechanical obstruction, but without a single site of obstruction demonstrable on imaging. Common causes include recent abdominal surgery, medications such as opiates, and electrolyte disturbances.

**Complete SBO:** Obstruction with no passage of luminal contents beyond the point of obstruction (Appendix A).

**Partial SBO:** Incomplete obstruction with luminal narrowing but some contents continue to pass through the intestine. This is distinguished from complete obstruction by the continued passage of bowel movements and flatus, and a non-peritonitic abdominal exam^3.

**Small bowel dilatation:** Luminal diameter of >3 cm.

**Transition zone:** Short segment area between dilated proximal bowel and decompressed distal bowel. Sometimes called a transition point and is radiographic evidence of SBO.

**Bowel compromise:** when there is ischemia or injury that has led to necrosis and/or perforation of the bowel wall.

**Adhesions:** Fibrous tissue that connects surfaces or organs within the peritoneal cavity that are normally separated. Such adhesions are the results of an adaptive healing response of the peritoneum upon tissue handling or contact with blood or purulence, but also caused by other conditions like radiotherapy, endometriosis, inflammation or local response to tumors.

**Virgin abdomen:** abdomen of a patient without prior surgery. Although there is no consensus in the literature about radiotherapy, known peritoneal inflammatory disease or primary abdominal wall hernias, in our study we will consider only those non-operated inside the definition.

Water Soluble Oral Contrast (WSOC) challenge: a combined diagnostic study and therapeutic intervention utilized in the evaluation and management of small bowel obstruction.

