### **Secondary Research Questions**

- What is the incidence and etiology of virgin abdomen SBO?
- What is the incidence of early postoperative SBO?
- What is the success rate for non-operative management?
- What is the prevalence of complications and treatment failure in the nonoperative management of SBO?
- Proportion of patients that underwent WSOC challenge, and under what indications?
- What are the Patient Related Outcomes results?

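### The prior-surgery item (PAS) leaves out caesarean section and abdominoplasty although virgin abdomen is limited to non-operated patients, and TLSE is blank after a single operation

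*Protocol*

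**What the plan says.** **Virgin abdomen.** The Definitions section describes it as the "abdomen of a patient without prior surgery". After naming radiotherapy, known peritoneal inflammatory disease and primary hernias as unsettled in the literature, it closes the matter: "in our study we will consider only those non-operated inside the definition". It makes no exception for caesarean section or abdominoplasty. The Secondary Research Questions then ask: "What is the incidence and etiology of virgin abdomen SBO".

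**Prior surgery on the form.** In Data Collection Instrument 4, the overall item on previous abdominal surgery (PAS) is answered "Yes/No (excludes abdominoplasty and cesarean section". The next item, the number of previous abdominal surgeries (NPS), is described as "Number (includes gyne and hernia surgeries". The category of the first operation (FSC) is "Predefined: CRS, GIS, HBPS, AWS, GIN, URO, VAS, AA (appendectomy", and its technique (FST) is free text.

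**Dates.** The first-surgery date (DFS) is labelled "Date First Surgery (if one also the last". The last-surgery date (DLS) is to be entered only when there was more than one abdominal operation. The time from last surgery to the episode (TLSE) is calculated as admission date (DOA) minus DLS, in years. A second secondary question asks for the incidence of early postoperative obstruction.

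**The concern.** A stated definition and the form item closest to it disagree about the same patients. None of the ten instruments has a virgin-abdomen field, and PAS is the only yes/no item on previous abdominal surgery in general. An analyst who takes PAS = No as the virgin-abdomen group would include women whose only operation was a caesarean section.

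The etiology half of the question is the more exposed. The Definitions section attributes adhesions to an "adaptive healing response of the peritoneum upon tissue handling or contact with blood or purulence". A caesarean section plausibly involves both handling and blood, so these patients could contribute post-surgical adhesive cases to a group meant to show what causes obstruction without surgery. The same argument is not made for abdominoplasty; there the problem is only that the definition makes no exception for it.

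The TLSE fault is separate and smaller. Used as built for the early postoperative question, it has no value for patients whose only operation was recent, and they would drop out.

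**Working it through.** The protocol gives no figure to reproduce here. The check applies the rules of Data Collection Instrument 4 literally, counting for the date fields only operations that PAS counts, and compares the result with the Definitions section.

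| Surgical history | By the definition | PAS | DLS | TLSE as written | With DFS as fallback |
|---|---|---|---|---|---|
| None | virgin | No | blank | blank | blank |
| Caesarean section only | operated | No | blank | blank | blank |
| Abdominoplasty only | operated | No | blank | blank | blank |
| One appendectomy, 18 days before admission | operated | Yes | blank | **blank** | 18/365.25 = 0.049 years |
| Two operations, the last 18 days before admission | operated | Yes | entered | 0.049 years | 0.049 years |

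Rows 2 and 3 are the PAS contradiction: on this reading they cannot be told apart from row 1. Row 4 is the TLSE fault.

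**Can other fields separate rows 1 and 2?** Possibly. NPS mentions gynaecological surgery, FST is free text, and FSC has the code GIN, presumably gynaecology. But the form does not say whether a caesarean section counts in NPS, nor whether NPS, FST and FSC are completed when PAS = No. Two centers could code the same patient differently.

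**Size of the PAS misclassification.** The document gives no shares, so every input is an assumption:

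- v = share of the cohort truly unoperated;
- s = share whose only operation was a caesarean section or abdominoplasty;
- r = fraction of s that NPS, FST or FSC reveals.

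Operated fraction of the recorded virgin group = s(1 − r) / (v + s(1 − r)).

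| v, s | r = 0 | r = 0.5 | r = 1 |
|---|---|---|---|
| 15%, 3% | 0.03/0.18 = 16.7% | 0.015/0.165 = 9.1% | 0% |
| 20%, 1% (lowest) | 0.01/0.21 = 4.8% | 0.005/0.205 = 2.4% | 0% |
| 10%, 5% (highest) | 0.05/0.15 = 33.3% | 0.025/0.125 = 20.0% | 0% |

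The apparent virgin-abdomen share is too high by s(1 − r); in the first row at r = 0 it reads 18% instead of 15%.

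**Size of the TLSE fault.** It follows from the rules alone: TLSE is blank for every patient with exactly one prior operation, and the interval can be rebuilt for each of them with DOA and DFS entered.

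**The case against.** The strongest reply is that the harm is conditional. Nothing in the protocol equates virgin abdomen with PAS = No, or early postoperative obstruction with a TLSE cut-off, and such derivations commonly belong in a statistical analysis plan, which is not at hand. NPS = 0 would be an equally general marker of a non-operated patient and carries no caesarean exclusion. The PAS wording may also be deliberate; then one sentence in the Definitions section would suffice. Local investigators may correct entries while collection is open. The illustrated range of 0% to 33.3% rests wholly on assumptions, and both points touch only secondary, descriptive questions in a hypothesis-generating audit. For early postoperative status, Data Collection Instrument 8 has an entry for the first postoperative month.

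Much of this stands: the consequence depends on how the fields are used, the numbers cannot establish severity, and the TLSE fault is minor and recoverable. What does not follow is that the contradiction disappears. NPS leaves the status of caesarean section open, under a label that repeats the term PAS has just narrowed. A later analysis plan can choose a rule but cannot restore a history that was never entered. If the exclusion was intended, the definition as written is wrong instead. The early postoperative entry in Instrument 8 is only one option in a list of reasons against a contrast challenge, so it is no general record of recent surgery.

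**Conclusion.** The point holds. By the protocol's own definition, PAS gives the wrong answer for patients whose only prior operation was a caesarean section or abdominoplasty, and TLSE as printed is empty after exactly one operation. Confidence is high in the textual conflict and lower in its consequence.

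The PAS effect on the virgin-abdomen results cannot be sized from the document: it is nil if other fields always reveal the operation, and could reach a third of the recorded group under the most unfavourable of the assumed inputs. PAS deserves correction at the form, because inconsistent coding across centers is hard to undo later. TLSE is a formula slip that loses no data as long as DFS is entered. No primary research question depends on either field.

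**What to change.** 1. Let PAS cover any previous abdominal or pelvic operation including caesarean section, or keep PAS as it is and add one yes/no item for caesarean section and one for abdominoplasty. With separate items, derive virgin abdomen as a negative answer to all of them.
2. Word NPS to match, and state when FST and FSC are to be completed.
3. If leaving out either operation is intended, say so in the virgin-abdomen definition, so that definition and form agree and readers know who is in the group.
4. Define TLSE as DOA − DLS when NPS > 1, and as DOA − DFS when there was one operation.

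The cost is one reworded item or two new yes/no items, plus one corrected REDCap formula. None of it alters patient care. If collection has closed, TLSE can still be recomputed exactly. For PAS, derive virgin abdomen from all the surgical-history fields, query centers about patients coded PAS = No where possible, and report any misclassification that remains.

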# Data Collection Instrument 5 - Patient past SBO history

Past SBO history	Key Name	Data Type	Values
Previous SBO	PSBO	Binary	Yes/No
Number SBO Previous Episodes	NOE	Integer	Number
Date Last Episode	DLE	Date	dd/mm/yy
Previous WSOC challenge	PG	Binary	Yes/No
Previous Success Non-operative Treatment	PSCT	Binary	Yes/No
Previous Single Band Addesion	PSBA	Binary	Yes/No
Previous Small Bowel Resection	PSBR	Binary	Yes/No
Previous SBO Etiology	PSBOE	Chain	Previous SBO cause (Adhesions/Primary Hernia/Incisional Hernia/Parastomal Hernia/Bezoar/Radiation enteritis/Primary tumor

## Data Collection Instrument 6 - Current episode Symptoms and signs

Current Episode Clinical Symptoms	Key Name	Data Type	Values
Date Symptoms Start	DSS	Date; time	dd/mm/yy hh:mm
Abdominal Pain	SAP	Binary	Yes/No
Nausea	NAU	Binary	Yes/No
Vomiting	SV	Binary	Yes/No
Decreased Appetite	DAP	Binary	Yes/No
Constipation	SNPS	Binary	Yes/No (No pass stools)
Obstipation	SNPG	Binary	Yes/No (No pass gas)
Diarrhea	DIAR	Binary	Yes/No
Abdominal Distension	ADI	List	No/Mild/Severe
Peristalsis	SPE	List	Absent; Normal; Increased
Temperature	ST	Decimal	Number (ºC) i.e 36.5
Heart rate	SHR	Integer	Number
O2 Saturation	SO2	Integer	Number
Systolic Blood Pressure	SBP	Integer	Number
Respiratory rate	SRR	Integer	Number
SIRS Score	SIRS	Integer	Number (1-4) (temperature >38°C or <35°C, heart rate >90 beats/min, respiratory rate >20 breaths/min or PCO $_2$ < 32 mmHg, and WBC > 12000 cells/mm3 or <4000 cells/mm
SBO Type	SBOT	Binary	Complete/Incomplete (if SNPS or SNPG are Yes)

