## Data Collection Instrument 8 - Current episode, course evolution

Current Episode Course Evolution	Key Name	Data Type	Values
Severity Signs	CESS	Binary	Yes/No (if one is present: Unstable hemodynamics, peritonitis, sepsis (SIRS>2), acidosis, high lactate)
Ischemia Radiologic Signs	IRS	Binary	Yes/No (if one is YES: CTFF, CTDBE, CTP, CTPG, CTN, CTBWD>3mm, mesenteric edema)
Nasogastric/nasojejunal tube Insertion	NGTI	Binary	Yes/No
Initial NGT debit	INGTD	Integer	Number (mL)
Antibiotic Prophylaxis	PXATB	Binary	Yes/No
Antibiotic Treatment (if > 1 day)	TTATB	Binary	Yes/No
Treatment Fluids (ml/first 24h)	TTFL	Decimal	Number (ºC)
Treatmet Steroids	TTST	Binary	Yes/No
Total Urinary Output	TUO	Decimal	Number
WSOC Challenge	GGF	Binary	Yes/No
Exclusion Criteria for WSOC	GGFEC	List	No/Pregnancy/Inflamatory Bowel disease/Incarcerated hernia/Previous Radiotherapy/Mechanic inflammatory ileus/Tumor or carcinomatosis/Early postoperative period<1month/allergy to GGF)
Date WSOC	GGFD	Date; time	dd/mm/yy hh:mm
Post WSOC Vomiting	GGFPV	Binary	Yes/No
Post WSOC NGT debit	GGFNG	Decimal	Number (ºC)
Total Number of simple Abdominal X Ray	NXR	Integer	Number
Date Last Simple Abdominal X Ray	DLXR	Date; time	dd/mm/yy hh:mm
Last AX Ray WSOC in Stomach	LXR GGFS	Binary	Yes/No
Last AX Ray Deterioration	LXRD	Binary	Yes/No
Last AX Ray Colonic Air	LXRCA	Binary	Yes/No
Last AX Ray Colonic WSOC	LXRGGFC	Binary	Yes/No
Gas Pass	GP	Binary	Yes/No
Date Gas Pass	DGP	Date; time	dd/mm/yy hh:mm
Stools Pass	SP	Binary	Yes/No
Date Pass Stools	DSP	Date; time	dd/mm/yy hh:mm
Date Start Oral Feeding	DSOF	Date; time	dd/mm/yy hh:mm
Date Discharge from Emergency	DDE	Date; time	dd/mm/yy hh:mm
Emergency Department Lenght of Stay	EDLOS	Integer	Hours (calculation DDE-DOA)
Non-operative Treatment Success	COTS	Binary	Yes/No

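### The SIRS score counts four criteria but its listed range is 1–4, so a patient meeting none has no listed code, and stored fields can rebuild the score only approximately

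*Protocol*

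**What the plan says.** Protocol, Data Collection Instrument 6 (symptoms and signs), gives the SIRS score as an integer with the values "Number (1-4) (temperature >38°C or <35°C, heart rate >90 beats/min", followed by a respiratory criterion, "respiratory rate >20 breaths/min or PCO $_2$ < 32 mmHg", and a white-cell criterion, "WBC > 12000 cells/mm3 or <4000 cells/mm". That makes four criteria. No code for zero or none is given for this field anywhere in the Protocol.

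The components are stored as follows:

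- Temperature (ST), Instrument 6, decimal: "Number (ºC) i.e 36.5".
- Heart rate, Instrument 6: "Heart rate SHR Integer Number".
- Respiratory rate, Instrument 6: "Respiratory rate SRR Integer Number".
- White cell count, Instrument 7: "White Blood Cell Count WBC Integer Number x10³".
- PCO2: named only inside the SIRS definition, with no field of its own in any instrument.

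The one stated use of the score is in Instrument 8, where Severity Signs (CESS) is defined as "Yes/No (if one is present: Unstable hemodynamics, peritonitis, sepsis (SIRS>2), acidosis, high lactate".

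**The concern.** A patient with normal temperature, heart rate, respiratory rate and white cell count scores 0, and the form lists no such value. Sites can respond in different ways: enter 1, leave a blank, or enter 0 if the software lets them. The Protocol's primary objective is to look for variation in patients, management and outcomes across the cohort. A difference between centres that the form itself creates is therefore unwelcome, and blanks that arise this way would sit among the least sick patients rather than at random.

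The missing-data section excludes centres with more than 5% missing data in mandatory fields. It does not list those fields. If SIRS is one of them, the rule would push sites towards entering a false 1.

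The natural repair is to recompute the score from its components. The question is how far the stored fields allow that.

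**Working it through.** **1. Range.** Each criterion is met or not met, so there are 2^4 = 16 patterns. The number of patterns giving each score is:

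| Score | 0 | 1 | 2 | 3 | 4 |
|---|---|---|---|---|---|
| Patterns | 1 | 4 | 6 | 4 | 1 |

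The stated range of 1–4 is not reproduced. The count runs 0–4, and the pattern with nothing met is left out.

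**2. White cell count.** The criterion is above 12 or below 4 (thousands), and the stored value is a whole number. The Protocol gives no rounding rule, so three were checked:

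- Rounding to nearest: stored 12 covers 11.5 to just under 12.5, and stored 4 covers 3.5 to just under 4.5. Both are unresolved.
- Truncation: only stored 12 is unresolved.
- Rounding up: only stored 4 is unresolved.

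Every other stored integer settles the criterion. Taking the integer at face value gives false negatives only. For example, 12.4 rounded to 12 fails the upper test.

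**3. PCO2.** It is an alternative to a respiratory rate above 20. If the rate is above 20 the criterion is met whatever the PCO2. If it is 20 or less, the criterion stays open.

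**4. Rebuilding the score.** Temperature, heart rate and respiratory rate are each met or not, and white cell count is met, not met or unresolved: 2 × 2 × 2 × 3 = 24 stored patterns. The bounds on the true score are:

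- lowest = temperature + heart rate + respiratory rate + (1 if white cells met);
- highest = temperature + heart rate + 1 + (1 if white cells met or unresolved).

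Results, as counts of patterns and not of patients:

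- 8 of 24 give the exact score (respiratory rate above 20, white cells settled: 2 × 2 × 2).
- 22 of 24 are certainly 1 or more.
- 2 of 24 could be a true 0: nothing met with white cells clear (score 0 or 1), and nothing met with white cells unresolved (score 0 to 2).
- None proves a 0, since every true zero has a respiratory rate of 20 or less and an unknown PCO2.
- 8 of 24 leave open whether the score exceeds 2.

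**5. Effect on Severity Signs.** The sepsis component needs a score above 2. Neither 0 nor 1 exceeds 2, so entering 1 for a true 0 changes nothing there.

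**6. Size, by assumption only.** The Protocol gives no prevalences. Suppose the criteria are independent, with assumed prevalences for heart rate, respiratory criterion, temperature and white cells. Then P(0) is the product of the complements, and the true mean m is the sum of the prevalences. If zeros are entered as 1, the mean becomes m + P(0). If they are left blank, the mean of recorded scores becomes m / (1 − P(0)).

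| Assumed prevalences (%) | P(0) | True mean | Zeros as 1 | Zeros blank |
|---|---|---|---|---|
| 20 / 5 / 3 / 25 | 0.80 × 0.95 × 0.97 × 0.75 = 0.553 | 0.53 | 1.08 | 1.19 |
| 30 / 10 / 5 / 35 | 0.70 × 0.90 × 0.95 × 0.65 = 0.389 | 0.80 | 1.19 | 1.31 |
| 40 / 20 / 10 / 45 | 0.60 × 0.80 × 0.90 × 0.55 = 0.238 | 1.15 | 1.39 | 1.51 |

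On these inputs, centres with identical patients could report visibly different mean scores according to how they handle the missing code.

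**The case against.** The strongest reply is that this is a slip in one value range of a covariate, with little lost.

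- The components are stored. Temperature, heart rate, respiratory rate and most white cell values can be read back, so a recorded 1 or a blank can be checked. This stands. A reader might infer from the integer white cell field and the absent PCO2 that the score cannot be recovered at all; the documents do not support that. A rebuild is approximate, with known bounds.
- Nothing marks SIRS as a calculated field, whereas time since last surgery, emergency stay and time to surgery are marked so. The site presumably scores from source notes, with the exact white cell count and any blood gas at hand. This also stands: the two storage limits bear on a rebuilt score, not on the one the site enters.
- The Protocol lists 1–4 under values and does not say that the software enforces it. True, but if it does not, some sites will enter 0 and others 1 or nothing, which is no better.
- SIRS is not a listed outcome or research question, and other severity information is collected: AAST grade, lactate, CRP, creatinine, blood pressure, oxygen saturation and radiological signs of ischaemia. This stands and limits the consequence.

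It might also be said that a blank could be taken as zero. The Protocol states no such convention, and a blank of that kind could not be told apart from ordinary missing data. Elsewhere the form does list an absent level, for example for abdominal distension, CT type and reasons against the contrast challenge.

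**Conclusion.** The listed range is wrong for the score as defined: 0 is a possible value and has no code. Followed as written, the form turns patients meeting no criterion into blanks or false ones, and this affects the distribution of SIRS and its use as a baseline descriptor or adjuster. That conclusion needs no assumption beyond the definition itself.

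The effect is limited. The error touches only true zeros. Stored data narrow most of these to 0 or 1, or to 0 to 2 where the white cell count is unresolved, but cannot prove a zero.

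Two stronger inferences are not supported. One is that the error corrupts the sepsis component of Severity Signs; the range error alone cannot, although a rebuilt score could fall on the wrong side of that cut-off where white cells or PCO2 are unresolved. The other is that a known fraction of the cohort is affected. The 24% to 55% shown above rests wholly on assumed prevalences and independence, and the Protocol supplies no figure from which to derive it.

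**What to change.** In the data dictionary:

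1. Set the SIRS range to 0–4.
2. Store white cell count to one decimal place.
3. Optionally, calculate SIRS from temperature, heart rate, respiratory rate and white cell count. Either add an optional PCO2 field for values already measured in usual care, or state that the calculated score uses respiratory rate only.

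For records already entered, re-derive the score from ST, SHR, SRR and WBC, starting with blanks and entries of 1. Keep the site's entry alongside, because the site may have used a PCO2 or an exact white cell count that the database does not hold. Report the lowest and highest possible score where the respiratory rate is 20 or less or the stored white cell count is 12 or 4.

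The cost is one range, one field type and, if chosen, one calculation and one optional field, plus a scripted re-derivation. No visit, test or change of care is involved.
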